A Comparative Study on the Effect of Propolis and Dentine Bonding Agent in Treating Dentin Hypersensitivity: A Randomized Clinical Trial.

A RESEARCH PROPOSAL

By

[name]

MSc.DS Periodontology

Batch-I

Submitted to the Scientific Committee Dow University of Health Sciences

In partial fulfillment of the requirement For the Degree of

Master of Science - Dental Surgery

Periodontology

Dated: 30th May' 2018

Approved by: Board of Advanced Studies and Research (BASR)

RESEARCHER:

Name: [name]

Designation: Lecturer, Post graduate trainee

Department: Periodontology

Qualification: BDS, MSc.DS Trainee

Signature: _____

SUPERVISOR:

Name: [name]

Designation: Associate Professor

Department: Operative dentistry

Qualification: BDS, MSc, FCPS

Signature: _____

Table of Contents

Abstract:	Error! Bookmark not defined.
Chapter 1: Introduction	5
1.1 Background:	5
1.2 Literature Review:.....	7
1.3 Rationale of the Study:	10
1.4 Statement of Problem	10
1.5 Objectives	10
1.6 Hypothesis.	10
1.7 Operational Definitions:	11
Chapter 2: Methodology	12
2.1 Study Design:	12
2.2 Study Setting:	12
2.3 Study Duration:.....	12
2.4 Study Population:.....	12
2.4.1 Inclusion Criteria:	12
2.4.2 Exclusion Criteria:	13
2.5 Sample Size:.....	13
2.6 Sampling Technique:.....	14
2.7 Data Collection Procedure:.....	15
2.8 Data Analyses:.....	18
2.8.1 Study Variables:	18
2.8.2 Statistical Analysis.....	18
2.9 Ethical considerations:	18
2.10 Study Time line:.....	19
2.11 Budget:	19
Chapter 3: References:	20
APPENDIX-I.....	23
APPENDIX-II.....	24
APPENDIX-III.....	25

ABSTRACT

Background:

Dentin Hypersensitivity causes considerable pain and discomfort to an individual due to number of stimuli on exposed dentine. Different kinds of treatment strategies used in the resolution of Dentine hypersensitivity including the use of Propolis and Dentine Bonding Agent. No study has compared the efficacy of Propolis and Dentine Bonding Agent.

Objectives:

Comparison of the efficacy of Propolis and Dentine Bonding Agent in the treatment of Dentin Hypersensitivity.

Methods:

In this six month In- Vivo single blinded Randomized Clinical Study, a total number of 50 patients with complain of dentine hypersensitivity will be selected in two groups after taking consent. Group A and B will receive Propolis and Dentine Bonding Agent respectively by a trained operator. Recordings of Dentin Hypersensitivity will be obtained at Day 0, before and after the application of experimental agents, and also on Day 7, 15 and 30 by the Researcher. Response will be measured by Visual Analog Scale and Schiff Cold Air Sensitivity Scale. SPSS v.20 will used to analyze the data with level of significance set at $p < 0.05$. Friedman test will be applied to see the comparison within groups and Wilcoxon Signed Rank test will be used for Pairwise comparison. Mann Whitney U-Test will be applied for comparison between groups.

Key Words: Dentin Hypersensitivity, Propolis, Dentine Bonding Agent, Visual Analog Scale (VAS), Randomized Clinical Trail, Schiff Cold Air Sensitivity Scale

CHAPTER 1: INTRODUCTION

1.1 Background

Dentin Hypersensitivity can be defined as “Short acting, sharp pain that arises from exposed dentine due to various stimuli which is evaporative, thermal, osmotic, tactile and chemical and this pain cannot be attributed to any other form of dental defect, disease or pathology ^{1, 2}. Many other terms have been used to diagnose this typical common condition such as Dentine Sensitivity, Root sensitivity, cervical dentine sensitivity, cemental hypersensitivity but Dentin Hypersensitivity is the most often used term across the literature ³.

It has been reported that Dentin Hypersensitivity has multifactorial etiology and patients with periodontal and gingival disease usually encounter this painful condition ⁴. Dentin Hypersensitivity is initiated by denudation of dentinal tubules and several possible common causative factors which include gingival recession, pockets formation, acute and chronic inflammatory periodontal diseases, trauma, traumatic occlusal forces, parafunctional habits, acidic dietary components, abrasion, erosion, attrition, abfraction, tooth flexure, faulty and overzealous tooth brushing and periodontal procedures (specially Scaling and Root planing) lead to dentine exposure ⁵⁻⁷.

Dentin Hypersensitivity as reported by Canadian Advisory Board is Diagnosis of Exclusion ². It is diagnosed by means of self-report of sharp pain in vital tooth/ teeth by patients in response to external stimuli. ⁸.

A number of theories have been put forward to describe the mechanism of Dentin Hypersensitivity ⁹ but Brannstorm’s Hydrodynamic Theory is the most widely acceptable theory

and according to this theory, various stimuli cause changes in fluid movements in dentinal tubules either outwards or inwards, resulting in activation of nociceptors in pulpodentinal border, which ultimately lead to the characteristic short, sharp pain of Dentin Hypersensitivity^{10, 11}.

Variation in Prevalence of Dentin Hypersensitivity exists worldwide, ranging from 1.34% to 98%¹²⁻¹⁴. This presence of variation exists due to several reasons including different study designs, different selection criteria for each study sample, different diagnostic approaches and also type of setting where study was performed^{15, 16}.

As understanding of the cause of Dentin Hypersensitivity, the most appropriate treatment would be occlusion and blockage of exposed dentinal tubules and inhibition of the movement of intratubular fluid and the agents which have ability to seal and occlude the dentinal tubules are ideal for the treatment of Dentin Hypersensitivity^{17, 18}. Based on the mechanism of action, different agents have been widely used all around the world for the treatment of Dentine Hypersensitivity. Potassium nitrate used as a Nerve desensitizing agent and is widely used in dentifrices. Gluteraldehyde, Silver nitrate, Zinc chloride, Strontium chloride hexahydrate used as Protein precipitating agents and used in the treatment of Dentine Hypersensitivity by occluding patent tubules. Sodium fluoride, Stannous fluoride, Strontium chloride, Calcium phosphate, Calcium carbonate, Bio active glasses used as dentinal tubules Plugging agents. Fluoride varnishes, Oxalic acid and resin, Glass ionomer cements, Composites, Dentin bonding agents used as Dentine adhesive sealers. Lasers such as Neodymium:yttrium aluminum garnet (Nd-YAG) laser, GaAlAs (gallium-aluminium-arsenide laser), Erbium-YAG laser nowadays also used for the treatment of Dentin Hypersensitivity. Researches have been taking place on several other

materials among which Propolis is of special interest which has been used in homeopathic and herbal practices since long time ^{19,20}.

1.2 Literature Review

The properties of ideal desensitizing agent are that they should not irritate the pulp or cause discomfort on application or later on, easily applicable, effective long lastingly and it should not stained the teeth, as described by Grossman ²¹. Such treatment has not been discovered so far.

There is no Standard treatment till date for Dentine Hypersensitivity and this study aims to find one. Adhesive restoration materials and dentinal adhesives are considered dentinal tubule sealers and with the ability of sealing open dentinal tubules, it is used in the treatment of Dentin Hypersensitivity ²⁰. Reduction in Dentin Hypersensitivity with the application and penetration of resins for occlusion of dentinal tubules was suggested by Dayton et al and Nordenvell & Brannstorm ^{22, 23}. Various studies found the significant effect of Dentine Bonding Agent in the reduction of Dentin Hypersensitivity²⁴⁻²⁷. In a study conducted in Thailand, in 2008 by Tasanee Tengrungsun et al reported a significant reduction of Dentin Hypersensitivity by Dentine Bonding Agent and it was also superior to other experimental agent i.e. GaAIAs laser ²⁷. Prati C. et al reported a significantly decrease in Dentin Hypersensitivity with respect to the baseline values just after 10 minutes by Dentine Bonding Agent²⁴. Other studies also found a significant relief in the symptoms of Dentin Hypersensitivity when treated with Dentine Bonding Agent ²⁵, ²⁶. Duran et al in randomized split mouth study design concluded that Dentine Bonding Agents

significantly reduce the symptoms of Dentin Hypersensitivity and will be used in the treatment of Dentin Hypersensitivity ²⁸.

Dental adhesives technologies advance through many generations with changes in their mechanism, application technique, clinical effectiveness and number of steps. Seventh generation is the easiest and advanced adhesive system which is one step self-etch system combines the etchant, primer and bonding resin in a single application. This All in one adhesive system contains acidic functional monomers, hydrophobic and hydrophilic monomers, organic solvents and water into a single solution. ²⁹ Less postoperative sensitivity, reduced technique sensitivity and simplified clinical application are the advantages that made self-etching system a favorable system than etch and rinse system. 3M ESPE Scotchbond™ Universal Adhesive system is a Seventh generation one-step self-etch adhesive system which is indicated in sealing of dentinal tubules and this can be used in the treatment of Dentin Hypersensitivity.

Propolis is naturally occurring, resinous, non- toxic honey bee (*Apis mellifera*) product, collected from living plants. In homeopathic and herbal practice, it is widely used as anti-inflammatory, anti-septic and in treating different diseases as both local and systemic applications. The word “Propolis” is derived from Greek word “Pro” (in front of, at the entrance to) and “Polis” (city or community) and means a defender of a city or community. Bee glue is sometime used as a synonym for Propolis ³⁰. Due to its botanical origin, variation exists in Propolis composition therefore geographical location is a major determinant of its composition. It is generally composed of a mixture of 50- 60% resins and vegetable balsam , 35% waxes, 5-10% essentials and aromatic oils, 5- 10% Pollen, and 10- 15% other constituents such as Vitamin A, Vitamin B-complex, Vitamin E, amino acids, minerals, and other compounds and highly active biochemical substances known as Bioflavonoids. Bioflavonoids (flavones, flavonones and flavonols) are well

recognized plant extracts which have the properties of anti-bacterial, anti-viral, anti-inflammatory, anti-oxidative and anti-fungal³⁰⁻³².

There are various studies showing the uses of Propolis in dentistry and also in medicine and surgery. In medical science, Propolis is used as an anti-asthmatic, supports respiratory system, used to provide immunity against tumor cells, helps in tissue repair, diabetes control, photo inhibitor and for several other reasons³³⁻³⁵. In dentistry, it provides relief from denture ulcerations and stomatitis, halitosis, periodontal pocket and abscess. It is also used as intracanal medicament for antimicrobial activity, to prevent dental caries, for acceleration and healing of oral tissues, reduction in pulp inflammation and also in reduction of Dentin Hypersensitivity³⁵⁻³⁹.

There are various in vitro and in vivo studies which show the effect of Propolis in reduction of Dentin Hypersensitivity^{36, 40-48}. Almas K et al reported that Propolis is better in occluding dentinal tubules than Saline⁴¹. Torwane et al concluded that Propolis showed significant reduction in Dentin Hypersensitivity⁴⁷. Rana Al-Haj Hussain et al reported that Dentin Hypersensitivity which occurred due to chair-side tooth bleaching procedure could be successfully reduced by using Propolis.

In the previous studies, Propolis and Dentine Bonding Agents had a significant reduction in Dentine Hypersensitivity, but none of the study in the available literature had a comparison between Propolis and Seventh generation Dentine Bonding Agent for the treatment of Dentine Hypersensitivity. This study will test the Propolis and Seventh generation Dentine Bonding Agent as Desensitizing agents to find out which is more effective in treating Dentine Hypersensitivity.

1.3 Rationale of Study

Various researches have been done which show the significant effect of Propolis and Dentine Bonding Agents in the resolution of Dentin Hypersensitivity. But in the literature available, the comparative evaluation of Propolis and Dentine Bonding Agent has not been performed. So this study will compare the efficacy of Propolis with Dentine Bonding Agent in the treatment of Dentin Hypersensitivity. This study will further signify best regime in long-term success for the treatment of Dentin Hypersensitivity among the two options.

1.4 Statement of Problem

Use Propolis and Seventh generation Dentine Bonding Agent for the treatment of Dentine Hypersensitivity.

1.5 Objectives

The objective of this study is to explore which is more effective between Propolis and Seventh generation Dentine Bonding Agent for the treatment of Dentine Hypersensitivity.

1.6 Null Hypothesis

[figure not shown]
There is no difference in the efficacy of Propolis and Dentine Bonding Agent in the treatment of Dentin Hypersensitivity

1.7 Operational Definitions:

Dentine Hypersensitivity: Painful condition that arises from exposed vital dentine due to external stimulation of exposed dentinal tubules. ^{1,2}

Scaling and root debridement [SRD]: Scaling refers to the removal of plaque and calculus from the tooth surface whereas debridement is the removal of the necrotic cementum from the root surface.

Visual Analog Scale [VAS]: A Visual Analogue Scale (VAS) is a measurement instrument for subjective characteristics or attitudes that cannot be directly measured. This psychometric response scale is frequently used in epidemiologic and clinical research to measure the intensity or frequency of various symptoms.

Schiff cold air sensitivity scale⁴⁹: This scale is mainly used to evaluate subject response to a stimulus like air or evaporative. This scale is scored as follows:

1. Subject does not respond to air stimulus.
2. Subject responds to air stimulus but does not request discontinuation of stimulus.
3. Subject responds to air stimulus and requests discontinuation or moves from stimulus.
4. Subject responds to air stimulus, considers stimulus to be painful, and requests discontinuation of the stimulus.

CHAPTER 2: METHODOLOGY

2.1 Study Design:

A Single blinded Randomized Clinical Trial.

2.2 Study Setting:

This singled- centered Study will be conducted in Periodontology Department of Dow International Dental College (DIDC) of Dow University of Health Sciences (DUHS).

2.3 Study Duration:

Study will be conducted in six months after approval of the synopsis

2.4 Study Population:

2.4.1 Inclusion Criteria:

1. Subjects included in this study will be selected from outpatients attending the periodontology department of DIDC for the problem of Dentin Hypersensitivity.
2. Healthy males or females of 20- 45 years of age and will have at least 2 vital teeth with hypersensitivity on facial surfaces to evaporative stimulus.
3. Patients with Miller's Class I and II gingival recession will be included.
4. Patients with Score I of Silness and Loe Plaque Index⁵⁰.
5. The patients should have no systemic and mental illness.
6. Patients who used Flouride dentifrices for hypersensitivity but could not get relief from it.

2.4.2 Exclusion Criteria:

[figure not shown]
1. Patients with Carious, Cracked or Restored teeth, Abutment teeth used of Removable or Fixed Prosthesis and tooth with any other dental pathology.
2. Patients using analgesics, mood alteration drugs during last six months.
3. Smoker, pregnant and nursing mothers.
4. Patients using tooth whitening or bleaching agents in the last six months,
5. Patients undergoing orthodontic therapy and history of periodontal surgery during last six months.
6. Patients who refuse to give consent.
7. Patients who had Score 2 and 3 of Calculus index will also be excluded from this study.

2.5 Sample Size:

Total 50 patients will be carried out (25 in each group). Using PASS version 11, test for Pair means with 99% Confidence Interval and Power of test, mean difference of degree of sensitivity 1.8 (1.9 – 0.01) ²⁷ and 0.42 of Standard Deviation difference (3.35 – 2.93) ²⁷, sample size is 5 patients per group which we have increased to 25 patients per group.

2.6 Sampling Technique:

Diagnosis of Dentine Hypersensitivity will be made by obtaining detailed dental history and clinical examination of the patients prior to include in the study. History and clinical examination will eliminate and exclude the other forms and causes of Dentine Hypersensitivity which will not meet the inclusion criteria of this study. Definitive diagnosis of Dentine Hypersensitivity will be made by using Evaporative or Air blast stimulus from triple dental syringe on the sensitive surface. Then participants will be allocated to two groups through sealed envelope method. Groups will be named as Group A (Propolis) and Group B (Dentine Bonding Agent). It will only be disclosed out at the time of application of desensitizing agents by Operator.

2.7 Data Collection Procedure:

After explanation of the procedure, efficacy and safety of the materials used, possibilities of receiving either treatment options that is Propolis or Dentine Bonding Agent, the patients will be asked to sign a consent form at first (Appendix I & II). After the consent, a complete history will be obtained from the patient regarding his systemic health, medications, dental treatment and hygiene habits and smoking (Appendix III).

At baseline (Day 0), thorough oral prophylaxis will be done for all the patients which include Scaling & Root Debridement with Polishing and detailed oral hygiene instructions should be given. Scaling is recommended to remove plaque, calculus and food remnants so clean tooth surface will be available for application of Propolis and Dentine Bonding Agent. Subjects will be provided with kit containing same type of standard Toothpaste (Colgate[®] Maximum Cavity protection PLUS Sugar Acid Neutralizer[™]) and Toothbrush (Colgate[®] 360[°] Sensitive Pro-Relief[™]) for oral hygiene during research time. Proper tooth brushing technique will be explained and demonstrated to each and every patient. Dietary counseling will also be done in order to avoid intake of excessive acids during study period.

After debridement, pretreatment assessment will be done by trained examiner. To evaluate and assess Dentin Hypersensitivity, Evaporative stimulus (controlled air blast stimulus) will be used from dental triple syringe or air water syringe which will be directed onto the affected area from a distance of 10mm for up to two seconds with complete isolation of the adjacent teeth by cotton roll. Responses will be measured on 10 cm line on Visual Analog Scale (VAS)⁵² which will be scored as 0 (No Pain), 1-3 (Mild Pain), 4-6 (Moderate Pain) and 7-10 (Severe Pain). Another scale names Schiff Cold Air Sensitivity Scale⁴⁹ will be used to measure response graded as 0, 1,

2, 3. Responses from all patients will be recorded by a single examiner, who will be blind to the applied desensitizing agents.

The patients will be allocated in to two respected groups, according to randomization by the process of sealed envelopes. The groups will be divided according to the desensitizing agents. Group A includes patients that will receive Propolis as a treating agent. Propolis obtained from Margalla hills, Islamabad by NARC (National Agriculture Research Council, Islamabad). Plant source origin is *Acacia modesta* and *Apis mellifera* bees collect it. The 30% ethanolic extract of Propolis from raw Propolis will be obtained in Pakistan Council of Scientific & Industrial Research (PCSIR) by dissolving the Propolis in 95% Ethanol and straining out the precipitate. Group B includes patients that will receive Dentine Bonding Agent (Scotchbond™ Universal Adhesive, 3M ESPE Dental Products, St. Paul, MN, USA).

Only the Principal Investigator will be blind to the intervention given to the participants. Application of desensitizing agents to participants will be carried out by trained and experienced operator and it will only be disclosed to operator at the time of application. Operator will inform the participant about the intervention before applying and patients will not be blinded. Desensitizing agents will be applied on day 0 (baseline). Complete isolation of proximal sides from hypersensitive teeth will be done by using cotton rolls. Hypersensitive teeth surfaces will be dried by cotton pellets. Propolis will then be applied by brush on sensitive surfaces and left undisturbed for 60 seconds to let it dry. Application of Dentine Bonding Agent on sensitive surfaces will be applied single coated for 20 seconds, gently apply air for 5 seconds and cure for 10 seconds (as manufacturer's instructions). For Score 4-6 s(Moderate Pain) & 7-10 (Severe Pain) on VAS and grade 3 (Subject responds to air stimulus, considers stimulus to be painful and requests discontinuation of stimulus) of Schiff Cold Air Sensitivity Scale, application of Propolis

and Dentine Bonding Agent will be applied under Local Anesthesia and response will be recorded on next day.

Care should be taken to ensure that none of the products will touch other areas of oral mucosa. Patients will be instructed not to rinse, drink or eat for half an hour after the application of treatment agents and avoid using any desensitizing dentifrices during the course of investigation.

The clinical evaluation of Dentin Hypersensitivity will be done before and after the application of Desensitizing agents at baseline (Day 0), and also on day of re-assessment at 7th, 15th and 30th day (Appendix III).

2.8 Data Analysis:

2.8.1 Study Variables:

Independent Variables:

- Sessions (Days)
- Groups

Dependent Variables:

- Visual Analog Scale (VAS)
- Schiff Cold Air Sensitivity Scale

2.8.2 Statistical Analyses:

Statistical Package for Social Sciences (SPSS) version 20 will be used to analyze the data. The level of statically significance will be set at $p < 0.05$. to see the comparison within groups, Friedman test will be applied. For Pairwise comparison, Wilcoxon Signed Ranked Test will be used. For between groups comparison, Mann- Whitney U- Test will be applied.

2.9 Ethical considerations:

The present study will be non-offensive and secure for the participants. Participants will be selected voluntarily and the informed consent is mandatory to be signed. The participant's data will be kept confidential. The participants will not be forced to continue the study if they are unwilling to continue after selection. Final results will be disclosed to the patients once the study has completed. The desensitizing agents and procedures that will be used in present study were

tested before in many other studies and there are no reported incidences of adverse outcome and complexity regarding their use.

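### Section 2.5 gives the planning difference as 1.8 but shows it as 1.9 – 0.01, which is 1.89, and does not say what the two inputs are

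*Combined protocol and SAP*

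**What the plan says.** Section 2.5 (Sample Size) puts the whole calculation into one sentence. It uses a "test for Pair means" in PASS "with 99% Confidence Interval and Power of test". The effect is a "mean difference of degree of sensitivity 1.8 (1.9 – 0.01") and the spread is "0.42 of Standard Deviation difference (3.35 – 2.93"). Both are cited to reference 27, a comparison of a laser with a dentin bonding agent. The conclusion is that the "sample size is 5 patients per group which we have increased to 25 patients per group".

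No other treatment difference is given anywhere in the document. Section 2.5 does not say whether 1.9 and 0.01 are mean scores or mean changes, what scale or visit they come from, or which SD belongs to which mean. For this trial's own outcome, section 2.7 says: "Responses will be measured on 10 cm line on Visual Analog Scale". It scores that line from 0 to 10. Section 2.8.2 sets significance at 0.05 and names the Mann-Whitney test for the comparison between groups.

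**The concern.** The stated difference does not equal the subtraction printed beside it. A reader cannot tell whether 1.8 is the intended figure with its working misprinted, or whether the working is right and 1.8 is wrong.

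A mean of 0.01 also looks odd next to SDs near 3, which raises the question of what kind of quantity it is.

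At stake is the basis for any restated size or power. The same sentence has larger faults: the SD of 0.42 is a difference between two SDs, and a paired calculation is used for two separate groups. Someone who repairs only those would carry 1.8 forward as the effect size without knowing whether it is right, or whether it is a difference between two like quantities.

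**Working it through.** **Inputs, all from section 2.5 unless noted.** Difference 1.8, shown as 1.9 – 0.01. SD 0.42, shown as 3.35 – 2.93. Paired means. The 99% is read as two-sided alpha 0.01 and power 0.99; this is an assumption, because the wording is loose. Calculated size 5 per group, raised to 25. VAS range 0-10 (section 2.7). Analysis alpha 0.05 (section 2.8.2).

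**1. Reproduce the plan's figure.** For a paired t-test the noncentrality is difference × √n / SD, with n – 1 degrees of freedom. At 1.8, SD 0.42 and alpha 0.01:
- n = 4: power 0.893
- n = 5: power 0.9955

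The smallest n reaching 0.99 is 5, so the plan's figure is reproduced with 1.8.

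**2. Check the subtraction.** 1.9 – 0.01 = 1.89. The printed 1.8 results if 1.89 was truncated to one decimal, or if 0.01 stands for 0.1 (1.9 – 0.1 = 1.8). A misprint in 1.9 is also possible. The document does not settle which.

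**3. Effect of the slip on the plan's own method.** At 1.89 with everything else unchanged, n = 4 gives 0.918 and n = 5 gives 0.9977. The answer is still 5.

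**4. Could 0.01 be a raw mean score?** On a scale from 0 to U, a mean m allows an SD of at most √(m(U – m)).
- U = 10, m = 0.01: √(0.01 × 9.99) = 0.32
- U = 10, m = 0.1: √(0.1 × 9.9) = 0.99
- U = 3, m = 0.01: 0.17
- U = 100, m = 0.01: 1.00

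The printed SDs are 3.35 and 2.93. Read as a raw score on any of these scales, 0.01 goes with neither, and on 0-10 the repaired value 0.1 does not either. The bound needs values that cannot fall below zero. A change score can be negative, and a mean change near zero with an SD near 3 is quite possible.

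**5. Power of 25 per group as a two-group comparison.** Pooled SD = √((3.35² + 2.93²)/2) = √((11.2225 + 8.5849)/2) = 3.15. For a two-sample t-test at two-sided 5%, the noncentrality is difference / (SD × √(2/25)).

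| SD used | Power at 1.8 | Power at 1.89 |
|---|---|---|
| 2.93 | 57% | 61% |
| 3.15 (pooled) | 51% | 55% |
| 3.35 | 46% | 50% |

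The t-test stands in here for the planned Mann-Whitney test.

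**The case against.** The strongest reply is that the slip changes nothing. The plan's method gives 5 at either value, the 25 per group is a plain increase from 5 and was not derived from 1.8, and moving from 1.8 to 1.89 slightly raises power. All of that stands. The fall from above 99% to about half comes from replacing 0.42 with an actual SD and from comparing two groups, not from correcting the subtraction. It is also fair that only reference 27 can show which figure is wrong.

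Two stronger readings are tempting, and the document supports neither.

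- A reader might infer that 0.01 is simply impossible beside these SDs. That holds only for raw non-negative scores. Section 2.5 does not say they are raw scores, and its paired-means setting is compatible with within-patient changes. The 10 cm line is this trial's scale and is not shown to be the source's.
- A reader might infer that, if 1.9 is a correct 0-10 score, the other mean must be at least 0.95 (the lowest mean that allows an SD of 2.93), so the difference is capped at 1.9 – 0.95 = 0.95 and power is very low. A floor on the other mean does not cap the difference. On 0-10, an SD of 2.93 allows any mean from 0.95 to 9.05. A mean of 5, for example, gives 5 – 1.9 = 3.1 and about 93% power with 25 per group and the pooled SD.

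What survives the reply is that a wrong figure sits in the only planning difference, with its inputs unlabelled.

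**Conclusion.** The subtraction is wrong as printed, and this is certain: 1.9 – 0.01 is 1.89, so 1.8 or one of its inputs must be corrected. It is not shown that 1.8 itself is the wrong number. The conflict between 0.01 and the SDs is conditional on raw scores on a 0-10 scale and disappears for change scores.

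Taken alone the error is small and leaves the calculated 5 per group as it is. Its weight comes from being the sole effect size that any repaired calculation will inherit. That repaired calculation gives about 51% power at 1.8 and 55% at 1.89. These figures assume that the printed SDs apply to the compared quantity in each group, equal groups of 25 with no losses, and a two-sided 5% t-test. They show where the plan stands on its own numbers. They are not a forecast, because the true inputs are not known from the document.

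**What to change.** 1. Check 1.9, 0.01, 3.35 and 2.93 against reference 27. For each, state whether it is a score or a change from baseline, on what scale, at which visit and for which group.
2. Correct 1.8 to 1.89, or correct whichever input is wrong. If 1.9 and 0.01 turn out not to be means of the same quantity, do not use their difference for planning.
3. Restate the power of 25 per group at the corrected difference, as a two-group comparison at the 0.05 level of section 2.8.2, with an actual SD in place of 0.42.

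The cost is one rewritten sentence in section 2.5 and one recalculation. With the printed SDs, the stated power will be less favourable than the current text implies. Whether 25 per group is then enough can be judged only once the inputs are confirmed.

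### The sample size calculation in section 2.5 uses the difference between two SDs as an SD, so the 5 per group is invalid and 25 per group has no stated basis

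*Combined protocol and SAP*

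**What the plan says.** Section 2.5 describes a PASS 11 calculation as a "test for Pair means with 99% Confidence Interval and Power of test". Its inputs are a "mean difference of degree of sensitivity 1.8 (1.9 – 0.01") and "0.42 of Standard Deviation difference (3.35 – 2.93"), all four figures cited to reference 27. The result is that the "sample size is 5 patients per group which we have increased to 25 patients per group". Nothing else is offered for the 25: no power, dropout allowance, precision target or detectable difference.

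The rest of the plan describes a parallel-group comparison:

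- Section 1.6, null hypothesis: "There is no difference in the efficacy of Propolis and Dentine Bonding Agent in the treatment of Dentin Hypersensitivity".
- Section 2.6: "Then participants will be allocated to two groups through sealed envelope method".
- Section 2.7: "Responses will be measured on 10 cm line on Visual Analog Scale (VAS"). The Schiff scale is recorded as well.
- Section 2.8.2: "The level of statically significance will be set at" p < 0.05. The groups are compared by Mann-Whitney; Friedman and Wilcoxon signed-rank tests serve the within-group comparisons.

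**The concern.** A sample size for a difference in means needs the SD of the quantity being compared. Section 2.5 shows how its SD was obtained: one reported SD was subtracted from another. That is not an SD of anything measured on patients, and 0.42 is about one seventh to one eighth of either figure it came from (2.93/0.42 = 7.0; 3.35/0.42 = 8.0).

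The calculation is also for paired means, although the hypothesis concerns different patients in two groups, and its 99% basis does not match the 0.05 level of the analysis.

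What is at stake is the reading of the result. As written, the trial appears to enrol five times the number needed for very high power. If that margin does not exist, a non-significant comparison could be taken as equal efficacy when the trial had little chance of showing a difference of 1.8 points.

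**Working it through.** **1. Reproducing the 5.** Inputs from section 2.5: difference 1.8, SD 0.42, alpha 0.01 (from the 99% confidence level, two-sided assumed), power 99%. For a paired t test the noncentrality is (1.8/0.42)·√n on n − 1 degrees of freedom. Power is 89.3% at n = 4 and 99.5% at n = 5, so n = 5. With 1.89 in place of 1.8 it is 91.8% and 99.8%, again n = 5. So 0.42 was entered as the SD of the differences.

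**2. When 0.42 would be correct.** SD of a paired difference = √(3.35² + 2.93² − 2r·3.35·2.93):

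| r | 0 | 0.5 | 0.7 | 0.9 | 1 |
|---|---|---|---|---|---|
| SD | 4.45 | 3.16 | 2.46 | 1.46 | 0.42 |

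Only r = 1 gives 0.42.

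**3. Does the choice of test explain the 5?** No. A two-sample t test with SD 0.42 and alpha 0.01 has power 95.5% at 4 and 99.6% at 5 per group, so it also gives 5. The SD is the root of the error.

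**4. What the cited figures could mean.** Section 2.5 gives no scale or time point, and does not say whether the figures are scores or changes, or groups or times. If 1.9 and 0.01 are the means belonging to these SDs, they are not raw 0–10 scores: a 0–10 score with mean 0.01 has SD at most √(0.01 × 9.99) = 0.32. Two readings are therefore carried forward, both for 1.8 points, two independent groups and two-sided alpha 0.05. Two-sample t power uses noncentrality (1.8/SD)·√(n/2) on 2n − 2 degrees of freedom.

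*Reading A: 3.35 and 2.93 are between-patient SDs of the VAS outcome compared (a change, or a score to which the cited means do not belong).* Pooled SD = √((3.35² + 2.93²)/2) = 3.15. SDs 2.0 and 2.5 are assumptions, added for range.

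| SD | Power, 25 per group | Power, 20 per group | Detectable with 80% power, 25 per group | n per group for 80% power |
|---|---|---|---|---|
| 2.0 | 88% | 79% | 1.6 | 21 |
| 2.5 | 70% | 60% | 2.0 | 32 |
| 2.93 | 57% | 47% | 2.4 | 43 |
| 3.15 | 51% | 42% | 2.55 | 49 |
| 3.35 | 46% | 38% | 2.7 | 56 |

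With 25 per group, 80% power for 1.8 points needs an SD of 2.2 or less. Using 1.89 points, power at the three document-based SDs is 61%, 55% and 50%.

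*Reading B: they are SDs at two time points, and changes are compared between groups.*

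| r | SD of change | Power, 25 per group | n per group for 80% power |
|---|---|---|---|
| 0 | 4.45 | 29% | 97 |
| 0.5 | 3.16 | 51% | 50 |
| 0.7 | 2.46 | 72% | 31 |
| 0.9 | 1.46 | 99% | 12 |

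Power reaches 80% only if r is about 0.76 or more.

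**5. Mann-Whitney instead of t.** For simulated normal data (20,000 runs, 25 per group), Mann-Whitney power is 85%, 67%, 54%, 48% and 43% at the five SDs of Reading A, about 2 to 3 points below the t test. For bounded, skewed scores it depends on shape. With rounded 0–10 scores of an assumed beta shape and SD 3.15, it was 85% for means 1.5 and 3.3, 73% for 2.0 and 3.8, and 50% for 4.0 and 5.8. With SD 2.0 it was 94% for means 1.5 and 3.3, against 88% for the t test.

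**6. Smaller slips.** 1.9 − 0.01 = 1.89, not 1.8.

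**The case against.** - **The subtraction is correct and 5 follows from the inputs.** True. The fault is in what was entered, and the paired-versus-independent mismatch on its own would not have changed the 5.
- **The plan has paired tests.** The within-group Wilcoxon tests may explain why a paired calculation was chosen, but they do not rescue it. At alpha 0.01 and 99% power, a paired test for 1.8 points needs 20 patients at r = 0.9, 78 at r = 0.5 and 151 at r = 0.
- **The source is not available and power could be anywhere from 29% to 99%.** This stands: the case is that 25 is unsupported, not that it is inadequate. But a plan whose power cannot be placed within that range does not justify its sample size.
- **Reading A may not apply.** The bound of 0.32 does rule out raw 0–10 scores if the cited means and SDs belong together. That is why no power figure should be written before the source is checked.
- **The skewed-score simulations use invented means and an extreme shape.** Partly fair. A mean of 1.5 with SD 3.15 on a 0–10 scale puts most scores at zero, so the 85% is illustrative only. The direction also appears in the milder SD 2.0 case.
- **This is an exploratory student project enrolling five times the calculated number.** The multiple means nothing once the 5 is invalid, and section 1.6 states a hypothesis to be tested.

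**Conclusion.** The point holds and must be fixed. The plan's only sample size figure depends on using 0.42 as an SD, which is right only under perfect correlation, and on a paired calculation at a 99% level for a between-group comparison tested at 0.05. The 5 per group is invalid, and 25 per group is left without a demonstrated basis.

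For 80% power at 1.8 points, the required number is 43 to 56 per group under Reading A and 12 to 97 under Reading B (correlations 0.9 to 0). These figures take the document's label of 3.35 and 2.93 as SDs at face value, and assume a two-sample t test with everyone analysed. None of them applies to the Schiff scale. Confidence in the error itself is high; whether 25 is enough cannot be determined from the documents.

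**What to change.** Keep 25 per group. In section 2.5, delete the 5 per group, the 0.42 and the 99% basis, and either correct 1.8 to 1.89 or explain it. Give the real reason for choosing 25, such as feasibility if that is the case.

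Before writing any power figure, check reference 27 for the scale, the time point and the meaning of the four numbers (score or change; groups or times). Then state:

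> Sample size is 25 per group. For [outcome, score or change] at [time point], comparing two independent groups at two-sided alpha 0.05 with 25 analysed per group, two-sample t-test power for [1.8 or 1.89] points is [values] over SDs of [range with its source], and the difference detectable with 80% power is [values]. Mann-Whitney power is about 2 to 3 percentage points lower if the data are normal and can be clearly higher if scores are bunched near zero. Power is lower if fewer than 25 per group are analysed. No power is claimed for the Schiff scale.

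The Reading A table supplies the values only if the source shows between-patient VAS SDs. If it gives SDs at two time points and changes are compared, use the SD of change over a stated range of correlations.

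The cost is one source check and one rewritten paragraph, with no additional patients, visits or tests. The downside is a conditional and possibly less favourable power statement.
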